9.7.1. SCREENING PERIOD

Only adverse events, serious and not serious, directly related to the screening procedures will be captured during this period. Unrelated clinical adverse events that occur prior to enrollment will be considered part of the medical history.

9.7.2. ENROLLMENT PERIOD THROUGH END OF STUDY

All adverse events that occur from the time of enrollment will be recorded as follows:

- Serious Adverse Events (identified in **Section 9.2**) will be recorded until Day 60 after enrollment, death, or patient withdrawal of study consent, whichever occurs first.
- Non-serious adverse events will be recorded until end of study follow-up period after enrollment, death, patient withdrawal of study consent or until hospital discharge, whichever occurs first.

Any serious adverse event (regardless of relationship to the treatment) occurring from the time of enrollment through end of study must be reported to CytoPherx Inc, or designee, within 24 hours of knowledge of the event.

Each clinical trial site will be supplied with written SAE reporting

instructions, SAE reporting forms and contact information for reporting of serious adverse events.

For any AE that is ongoing at the time of the initial report, periodic follow-up information will be required until the adverse event is resolved or the patient is no longer in the study, whichever occurs first.

The Investigator is responsible for all adverse events reporting to the Institutional Review Board (IRB) according to the requirements of the IRB and for providing clinical trial monitors with all medical records needed to source-verify the adverse events.

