6.5 STUDY FOLLOW UP PERIOD

6.5.1 POST END OF STUDY TREATMENT PERIOD

This Study Follow Up period has been broken into five 24 hour time periods. It starts when the patient has reached 168 hours in the observation period or when the patient meets the termination criteria outlined in **Section 7.2**. It ends at 120 hours or ICU discharge, whichever comes first. Record the following data daily in the Study Follow-up Period unless otherwise noted:

- **Vital Signs/Physical Assessment**
 - Blood pressure, heart rate, temperature
 - Physical Exam (first 24 hours only)
 - Urine Output (from previous 24 hours)
 - Net fluid balance (from previous 24 hours)
- **Clinical Laboratory Tests (first 24 hours only)**
 - CBC with differential
 - BUN, Creatinine
 - Na, K, Cl, HCO₃, Ca, Mg, Ionized Ca, PO₄

- **Respiratory**
 - Status – Ventilator support (yes/no)
 - If on Vent: FiO₂
 - If on Vent with an arterial line: Arterial Blood Gas(first 24 hours only)
 - If on Vent without an arterial line: Arterial Blood Gas (if available, first 24 hours only)
- **Renal Replacement Therapy status**
 - RRT status
- **Other (Event Driven)**
 - Microbiology/culture data
 - Adverse Events
 - Acknowledgement (yes/no) to antibacterial agents administered to the patient.

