6.5.3 DAY 60 POST ENROLLMENT

This visit may be done via telephone call or office visit. Please record the following information on day 60 (+7 days) following enrollment:

- Presence / dates of mechanical ventilation (since last visit)
- Presence / dates of renal replacement therapy (since last visit)
- ICU discharge date
- Hospital discharge date
- Serious Adverse events (since last visit)
- Serum creatinine (if an office visit takes place)

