APPENDIX F – SCD-PED-01 Study Schedule of Events

	Baseline	Hr 0-24	Hr 25-48	Hr 49-72	Hr 73-96	Hr 97-120	Hr 121-144	Hr 145-168	Therapy End
Vital Signs/Physical Assessment									
Temperature , Body Weight (baseline only)	X	X	X	X	X	X	X	X	
Blood Pressure (if no bp, MAP acceptable), Heart Rate	X	X	X	X	X	X	X	X	
PRISM II Score	X								
Physical Exam	X								
Urine Output (previous 24 hours)	X	X	X	X	X	X	X	X	
Net Fluid Balance (previous 24 hours)		X	X	X	X	X	X	X	
Sepsis	X								
ICU Percent Fluid Overload at CRRT Initiation	X								
Clinical Laboratory Testing									
CBC with differential	X	q12h	q12h	q12h	q12h	q12h	q12h	q12h	
BUN/Creatinine	X	X	X	X	X	X	X	X	
Na, K, Cl, HCO ₃ , Ca, Mg, PO ₄ , Ionized Calcium	X	X	X	X	X	X	X	X	
ALT, AST, Bilirubin, ALP, TP, Albumin, Glucose	X	X	X	X	X	X	X	X	
PT, PTT, INR	X	X	X	X	X	X	X	X	
Urinalysis (if urine is available)	X								
Respiratory									
Arterial Blood Gas (pH, PaO ₂ , PaCO ₂) (if on vent)*	X	X	X	X	X	X	X	X	
Ventilator Settings (FiO ₂)	X	X	X	X	X	X	X	X	
Blood For Research									
Blood for Biomarkers	X		X(hr/48)		X(hr/96)		X(hr/144)		X
Extracorporeal Device Parameters									
CRRT (Settings- Event Driven)	X (hour 0)	X	X	X	X	X	X	X	
Post Filter Ionized Calcium	X (hour 0)	q1h until <0.40mmol/L; then q6h	q6h	q6h	q6h	q6h	q6h	q6h	
CRRT Device and SCD Performance (Event Driven)		X	X	X	X	X	X	X	
SCD 24hr. Daily Change		X	X	X	X	X	X	X	
Other (Event-Driven)									
Adverse Events	X	X	X	X	X	X	X	X	X
Critical Medications, Blood products (yes/no) per Appendix J	X	X	X	X	X	X	X	X	X
Diagnosis/Therapeutic Procedures	X	X	X	X	X	X	X	X	X
Microbiology/culture data	X	X	X	X	X	X	X	X	

*Required only if the presence of an A-line; see **Section 6.3** and **Section 6.4** for details

APPENDIX G – SCD-PED-01 Study Schedule of Events: Follow-up Period**Day 1 - 5 or until ICU discharge (whichever occurs first unless otherwise specified)**

Measurement	Hour 0 - 24	Hours 25 – 120 ¹
Vital Signs/Physical Assessment		
Blood pressure, temperature, and heart rate	X	X
Physical Exam	X	
Urine Output (from previous 24 hours)	X	X
Net Fluid Balance – (from previous 24 hours)	X	X
Clinical Laboratory Tests		
CBC with differential	X	
BUN/Creatinine	X	
Na, K, Cl, HCO ₃ , Ca, Mg, PO ₄ , Ionized Calcium	X	
Respiratory:		
Arterial Blood Gas (pH, PaO ₂ , PaCO ₂)	X	
Ventilator Settings (FiO ₂)	X	X
Other(event driven)		
Renal Replacement Therapy status	X	X
Microbiology/Culture Data	X	X
Adverse Events	X	X
Serious Adverse Event	X	X
Antibacterial Medications (yes/no)	X	X

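### Section 9.7.2 does not say which follow-up period ends non-serious adverse event recording, and under the likelier reading ICU discharge cuts it short in survivors who recover faster

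*Combined protocol and SAP*

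**What the plan says.** Section 9.7.2 has two recording rules. Serious adverse events "will be recorded until Day 60 after enrollment, death, or patient withdrawal of study consent, whichever occurs first". For the others the rule is "Non-serious adverse events will be recorded until end of study follow-up period after enrollment, death, patient withdrawal of study consent or until hospital discharge". The list closes with "patient withdrawal of study consent or until hospital discharge, whichever occurs first", so the earliest listed event ends recording. The section neither cites Section 6.5.1 nor defines the follow-up period it names.

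Section 6.5 carries the follow-up period in its title and has three parts:

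- Section 6.5.1 covers the days after treatment: "This Study Follow Up period has been broken into five 24 hour time periods". Adverse events are among the items to record. On the end of the period it says: "It ends at 120 hours or ICU discharge, whichever comes first".
- Sections 6.5.2 and 6.5.3 are the Day 28 and Day 60 contacts. For the latter: "Please record the following information on day 60 (+7 days) following enrollment". The only adverse event item at either contact is "Serious Adverse events (since last visit").

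Appendix G schedules the post-treatment period as "Day 1 - 5 or until ICU discharge (whichever occurs first unless otherwise specified") and lists both adverse events and serious adverse events. Appendix H covers Days 28 and 60 with serious events only. The synopsis follows each patient for 60 days from enrollment. Section 9.7 reports adverse events as counts per unit of device exposure time.

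**The concern.** Safety is the primary objective in the synopsis, and adverse events are the first-listed safety measure. Two things make the non-serious part of that record uncertain.

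First, the stop depends on what the follow-up period in Section 9.7.2 means. If it is the Section 6.5.1 period, the two sections agree but the hospital-discharge stop can never act. If it is the whole of Section 6.5, hospital discharge becomes a working stop, but no schedule then collects non-serious events after the Section 6.5.1 period. With up to 10 centers, different sites could apply different stops.

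Second, even if the shorter meaning is intended, ICU discharge is a sign of recovery and also ends recording. Survivors who leave the ICU soon after SCD are watched for less time, and their non-serious events on the ward in the following days are not collected. The DSMB is to judge incidence and timing of adverse events after 5, 10 and 16 patients, and in groups that small a few short windows can move the rate.

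**Working it through.** **Which reading the documents favor.** For the Section 6.5.1 period:

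- It is the only follow-up period given a start and an end.
- Sections 7.1, 7.2 and 7.4 start the follow-up period as soon as treatment or observation stops, and Section 7.3 describes it as following SCD.
- Appendix G uses the term for Days 1 to 5 and lists adverse events there; Appendix H keeps Days 28 and 60 apart.
- Appendix J limits medication capture in the follow-up period to antibacterials, which matches Section 6.5.1.
- In Section 9.7.2 the serious-event rule names Day 60, and the non-serious rule uses another term.

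For the 60-day reading:

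- The title of Section 6.5 covers Days 28 and 60 as well.
- The synopsis and Section 10 speak of 60 days of follow-up.
- Section 9.7.2 counts from enrollment, whereas the Section 6.5.1 period is counted from the end of observation.
- A hospital-discharge stop has a function only if recording can outlast the ICU stay.

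The first reading is better supported; the second is not excluded.

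**Longest windows, from observation start.** The plan's own figures reproduce: 5 × 24 = 120 hours, and 7 × 24 = 168 hours.

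- Reading A (Section 6.5.1): min(end of SCD + 120 h, ICU discharge, hospital discharge, death, withdrawal). Maximum: 168 + 120 = 288 h, and 288 / 24 = 12 days. Hospital discharge never binds, because it cannot precede ICU discharge.
- Reading B (60 days): min(day 60, hospital discharge, death, withdrawal). Maximum: about 60 days.
- Largest gap: about 60 − 12 = 48 days.

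**Illustrative children.** The documents give no discharge times, so those below are assumed. The last column applies the proposed stop: min(end of SCD + 120 h, hospital discharge, death, withdrawal). Windows are in days.

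| SCD | ICU discharge | Hospital discharge | A | B | Proposed |
|---|---|---|---|---|---|
| 48 h | day 3 | day 10 | 3 | 10 | 7 |
| 72 h | day 5 | day 15 | 5 | 15 | 8 |
| 72 h | day 30 | day 45 | 8 | 45 | 8 |
| 168 h | day 20 | day 40 | 12 | 40 | 12 |
| 168 h | in ICU to day 60 | day 60 | 12 | 60 | 12 |
| 96 h, death on day 4 | – | – | 4 | 4 | 4 |

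Under A, days recorded after treatment are 1, 2, 5, 5, 5 and 0. Under the proposed stop they are 5, 5, 5, 5, 5 and 0.

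**Does the device-exposure denominator correct this?** In these cases the ratio of window to exposure runs from 1.0 (4/4) to 2.7 (8/3) under A and from 1.0 to 15 (45/3) under B. Take the two children with 72 hours (3 days) of SCD. If both have the same event rate r per day observed, reading A reports 5r/3 for the one who leaves the ICU on day 5 and 8r/3 for the one who stays. The second is 8/5 of the first, although the underlying rate is identical. Dividing by exposure therefore does not adjust for unequal windows.

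**The case against.** The strongest reply is that the documents largely settle the meaning. Taking the earliest of the listed stops, and reading the follow-up period as that of Section 6.5.1, both sections give one stop. A reader might infer a flat contradiction between them; that is not supported. It is an ambiguity with a redundant clause, and the wide gap in days arises only on the less supported reading.

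The second reply is about scope, and it stands. A reader might infer that the primary safety count as a whole is at risk. No single count is defined as the primary endpoint. Serious events run to Day 60 whatever the discharge date, and under Section 9.2 they include death and important events such as a return to the ICU. SCD is given in the ICU, so events during device exposure are recorded on either reading. There is no concurrent arm, and the Evaluation Plan compares mortality and dialysis dependency with historical controls, not adverse event counts, so no between-arm contrast is biased.

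Third, a reader might infer that recording ends earliest in the children who improve fastest. Death and withdrawal also end it, so the shortest windows include some of the sickest children. The statement holds among survivors only.

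Last, limiting non-serious events to the ICU or five days can be defended for a pilot. That would carry more weight if the rule gave each child still in hospital the same five days. As written, the loss falls on children who have just come off an investigational device and left the ICU.

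**Conclusion.** The point holds in two limited parts. The stop in Section 9.7.2 is not tied to a defined period. The better reading gives at most 12 days from observation start, and the other up to about 60. Separately, and even on the better reading, ICU discharge can end non-serious recording at any time within the 120 hours after SCD, so post-treatment observation among survivors varies with recovery from almost none to five days. Per-exposure reporting does not repair that.

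The maxima rest on the plan's own hours; the individual windows rest on assumed discharge times.

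No number of lost events can be given. A reader might take the 199 − 28 = 171 non-serious events in the 35 patients of ARF-002 and scale them to the shorter window, or read the ratio of windows as a ratio of events. The documents do not support either step. ARF-002 enrolled adults (mean age 56.3), its recording window is not given, and events would have to accrue evenly on the device, after it and on the ward.

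**What to change.** Use one stop for non-serious adverse events in Sections 6.5.1 and 9.7.2 and Appendix G: from enrollment until 120 hours after the end of SCD treatment or hospital discharge, whichever is earlier, or until death or withdrawal of consent, on the ward as well as in the ICU. Keep ICU discharge as a stop only for vital signs, laboratory tests and ventilator data. Name the period explicitly in Section 9.7.2, so that the hospital-discharge stop has a function and sites have one rule.

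In Section 9.7, also report non-serious events per time under adverse event observation, beside the planned rate per device exposure. This is needed because early ends of therapy, hospital discharge and death still leave windows unequal.

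The change concerns data collection and reporting, not treatment. The cost is wording in these sections and some added chart review: 5 − 1 = 4 days for a child who leaves the ICU one day after SCD ends, never more than five, and none for a child who stays in the ICU for the full 120 hours.

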10. DATA SAFETY MONITORING BOARD

An independent Data Safety Monitoring Board (DSMB) will review safety results over the course of the study on a schedule set by CytoPherx, Inc. and the DSMB. The DSMB will comply with the FDA Guidance: “Guidance for Clinical Trial Sponsors on the Establishment and Operation of Clinical Trial Data Monitoring Committees”. The DSMB will be formed to provide scientific and medical feedback for the study.

The DSMB will focus on the following areas:

- *Performance* – to assess study conduct and compliance;
- *Effectiveness* – to assess mortality and dialysis dependency;
- *Safety* – to assess the incidence, severity, relationship, and timing of adverse events and to identify safety concerns; and
- *Context* – to assess the study relative to the AKI literature.

The DSMB will reflect the disciplines and medical specialties necessary to interpret the data from the clinical study and to fully evaluate participant safety. The SCD-PED-01 DSMB will be made up of at least 2 medical practitioners with expertise in AKI and critical care medicine. The DSMB will operate under a charter and will identify prospective data display specifications to conduct independent data reviews. The DSMB will make recommendations to the Sponsor to continue the study as planned or to stop the study due to safety. The DSMB will meet to perform safety evaluations and to provide feedback to the Sponsor at least annually as well as after 5, 10 and 16 of the cohort has completed 60 day follow-up. An efficacy evaluation to historical controls will be accomplished after all 16 enrolled patients have completed 60 day follow-up. The DSMB reserves the right to request more frequent evaluations.

11. PROTOCOL ANALYSIS / SCIENTIFIC SOUNDNESS

This study derives from the hypothesis that up to seven or less sequential 24 hour SCD treatments will improve survival in patients with AKI requiring CRRT as compared to historical data. Further, SCD therapy may reduce the duration of maintenance dialysis secondary to acute renal failure (ARF) due to acute kidney injury (AKI).

The precise mechanism of action of the SCD is becoming better understood and appears to be an immunomodulatory process which inhibits leukocyte activation, a trigger of systemic inflammatory response syndrome (SIRS) and multi-system organ failure. The modulation of the pro-inflammatory state is believed to also allow recovery of renal function in AKI and other organ failure. The cartridge in the presence of citrate anticoagulant acts as a selective cytopheretic device to sequester and inhibit potentially damaging circulating leukocytes.

Recent data have demonstrated, that the inflammatory response of neutrophils adhered to a polysulfone dialysis membrane in the presence of low iCa and citrate are released with a normalized apoptotic life span, compared to a delayed apoptotic rate promoted in systemic inflammation. Leukocytes, especially neutrophils, are major contributors to the pathogenesis and progression of clinical inflammatory disorders, including SIRS, sepsis, ischemia/reperfusion injury and ARDS. Further data have demonstrated that monocytes with a proinflammatory phenotype, binds more avidly than monocytes with a reparative phenotype to the membrane in low iCa environment. This selective binding results in a less inflammatory circulating monocyte population in disorders of inflammation. The protocol has been carefully constructed with precise AKI diagnostic criteria, CRRT or comparable mode treatment and definition of patient's age, need to tolerate citrate anticoagulation and placement in the ICU during SCD therapy. Patient exclusion criteria are also detailed so as to provide a well characterized and standardized patient population. Observational periods and a complete schedule of events in the protocol delineate specific efficacy measurements as required to test the study hypothesis, including bio-inflammatory assay markers, and WBC activation studies.

Besides the test of the hypothesis the study is focused on observable, empirical and laboratory determinations of patient safety while on the SCD. Previous human trials have been conducted on the SCD device and the protocol contains a review of AE and SAE data from all SCD human studies and findings from those studies contributed to constructing the investigative safety profile. Safety endpoint measures specified in the protocol include adverse events, laboratory safety parameters, vital signs, ventilation status and hemodynamic variables. Device integrity and performance measurements are also defined as are circumstances which demand premature termination of SCD treatment.

Prolonged exposure to the SCD is anticipated to result in superior outcomes, although as noted above, this pilot study is not designed to assess for efficacy. However, we understand that a minimum amount of exposure to the SCD will be required for an appropriate safety analysis and for making any inference regarding efficacy. The ppCRRT experience demonstrated that the majority of patients (201/370) received CRRT for 1 to 7 days and exhibited 65% survival (Symons et al CJASN 2007 Table7). Assuming our trial includes patients with similar illness severity, we have established a 72 minimum number of hours a patient will be treated with the SCD to be included in the final outcome analysis.

This trial is an early safety efficacy study but is not powered for statistical significance. Insights into a comparison of historical controls matched to SCD treated patients will utilize the ppCRRT Registry to match for: etiology of AKI, co-morbidities, CRRT modality, dose and form of anticoagulant, adverse events. [10].

The ppCRRT Registry has data fields for the primary reason for CRRT, including AKI and its cause, as well as co-morbidities which will be matched for primary organ system involvement. The CRRT modality was evenly distributed between convective and diffusive modality, with 60% of the convective modalities provided as CVVH and 40% as CVVHDF. The anticoagulant protocol will be standardized with ACD-A/CaCl₂ and all centers used the same protocol in ppCRRT Registry as outlined in this study protocol. Thus, the ppCRRT Registry dataset will be able to be matched to our study patient cohort. Also as noted above, patients will be matched for age, size and PRISM II score.

The Prospective Pediatric CRRT (ppCRRT) database will be used as a control for the CRRT treatment related factors including: patient age, gender, primary cause of AKI, total treatment duration, CRRT modality (CVVH, CVVHD, CVVHDF), CRRT small solute clearance (ml/1.73m²/hour), baseline estimated GFR (using the original Schwartz formula, which was used in the ppCRRT), urine output in the 24 hours prior to CRRT initiation (ml/kg/hour), percent fluid overload at CRRT initiation based on admission ICU weight, vasoactive medication number at time of CRRT initiation and mean airway pressure at CRRT initiation.

An additional analysis will also evaluate patients who have achieved targeted iCa levels during 90% of treatment time and those who do not.

In summary this protocol meets all criteria necessary for clinical scientific inquiry related to a test of hypothesis in a well monitored environment focused on patient safety during the conduct of the study. Basic statistics will be performed on the data sets along with historical data comparisons and subjected to subset analysis where appropriate. The results will help to guide the design of a future pivotal study of this device.

The rational for therapy, study objectives and endpoints, design, inclusion and exclusion criteria are explicitly defined. Patient safety parameters are well documented including safety reporting, safety observations and assays, procedures for patient withdrawal and study discontinuation criteria along with monitoring device integrity and performance. Lastly, a review of all prior SCD human study safety data is included in the protocol for full disclosure to study investigators and the informed consent document includes a full description of all known and potential risks of the device treatment.

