	
17. Dry weight of <15 kg.18. Platelet count <15,000/mm³ at time of screening.19. Concurrent enrollment in another interventional clinical trial. Patients enrolled in clinical trials where only measurements and/or samples are taken (NO TEST DEVICE OR TEST DRUG USED) are allowed to participate.20. Use of any other Investigational drug or device within the previous 30 days.
Evaluation Plan	The primary evaluation of this study will be safety and all-cause mortality or dialysis dependency through 60 days post-enrollment. Additional endpoints will be time on CRRT, total ICU and hospital days. Mortality and dialysis dependency rates will be compared to historical controls.

LIST OF ABBREVIATIONS

[figure not shown]
AE	Adverse Event
AKI	Acute Kidney Injury
ARDS	Acute Respiratory Distress Syndrome
ARF	Acute Renal Failure
ATN	Acute Tubular Necrosis
BW	Body Weight
iCa	Ionized Calcium
CBC	Complete Blood Count
CRF	Case Report Form
CRRT	Continuous Renal Replacement Therapy
CTICU	Cardiothoracic Intensive Care Unit
CVVH	Continuous Veno-Venous Hemofiltration
CVVHD	Continuous Veno-Venous Hemodialysis
CVVHDF	Continuous Veno-Venous Hemodiafiltration
ECS	Extra Capillary Space
ICU	Intensive Care Unit
MICU	Medical Intensive Care Unit
nriCa	Non Recommended Ionized Calcium Range
ppCRRT	Prospective Pediatric CRRT Registry
PRISM	Pediatric Risk of Mortality
RAD	Renal Assist Device
riCa	Recommended Ionized Calcium Range
SAE	Serious Adverse Event
SCD	Selective Cytopheretic Device
SICU	Surgical Intensive Care Unit
SIRS	Systemic Inflammatory Response Syndrome
SOFA	Sequential Organ Failure Assessment
WBC	White Blood Cell
UADE	Unanticipated Adverse Device Effect

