3. PILOT STUDY (PROTOCOL SCD-PED-01) OBJECTIVES AND ENDPOINTS

3.1 PRIMARY OBJECTIVE

To evaluate the safety of the SCD treatment up to seven consecutive 24 hour SCD treatments compared to historic data on in-hospital mortality and on all cause mortality and dialysis dependency at day 28, and day 60 in the pediatric AKI population being treated with Continuous Renal Replacement Therapy (CVVH, CVVHD, or CVVHDF) with regional citrate anticoagulation.

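### The final outcome analysis keeps only patients with at least 72 hours of SCD, a condition settled after treatment starts, so mortality and dialysis-dependency results are open to selection bias of unknown direction

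*Combined protocol and SAP*

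**What the plan says.** Section 11 (Protocol Analysis / Scientific Soundness) sets the rule: "we have established a 72 minimum number of hours a patient will be treated with the SCD to be included in the final outcome analysis". The sentences before it give the reason. Longer exposure is expected to do better, and "a minimum amount of exposure to the SCD will be required for an appropriate safety analysis" and for any inference about efficacy. The support cited is that 201 of 370 registry patients had CRRT for 1 to 7 days, with 65% survival.

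The outcomes concerned are prominent. The synopsis Evaluation Plan states: "The primary evaluation of this study will be safety and all-cause mortality or dialysis dependency through 60 days post-enrollment". Section 3.1 words the primary objective as safety "compared to historic data on in-hospital mortality and on all cause mortality and dialysis dependency at day 28, and day 60", although the synopsis lists mortality and dialysis dependency under the secondary objective.

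Section 10 says "An efficacy evaluation to historical controls will be accomplished after all 16 enrolled patients have completed 60 day follow-up". That fixes when the comparison is made, not who is in it. Appendix D defines mortality and dialysis dependency without naming an analysis set. It does name one for renal recovery, namely subjects alive at day 28.

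For the registry comparison, Section 11 will "match for: etiology of AKI, co-morbidities, CRRT modality, dose and form of anticoagulant, adverse events". A second list of control factors includes "primary cause of AKI, total treatment duration, CRRT modality". Neither list states a 72-hour condition for the controls.

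**The concern.** A rule for who is counted should rest on something fixed when treatment starts. Time on the SCD is not fixed then. Section 7.3 allows SCD to end early for improvement, SCD-related events, SCD failure, death, withdrawal of life support and failure to reach the circuit calcium target in the first 12 hours of CRRT. Section 7.1 ends the observation period after too long an interruption. Several of these reasons are the endpoint itself or close to it. A child who dies at hour 40 is removed from the mortality result, and so is a child who recovers and comes off CRRT on day 2.

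Both the absolute rates and the registry comparison can therefore move with who leaves early, whatever the device does. The study has one arm and no randomisation, so the choice of analysis set carries much of the result. Section 11 says of the study: "The results will help to guide the design of a future pivotal study of this device". Pivotal-trial assumptions drawn from a selected subset would carry the selection forward.

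**Working it through.** **The plan's own figure.** 201/370 = 54.3%, which agrees with the word majority. The 1-to-7-day band includes patients with 24 to 72 hours of CRRT, so it neither yields a 72-hour cut-off nor shows that few patients fall below it. The plan gives no power or sample-size calculation to reproduce.

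**Inputs.** True mortality p = 35%, the complement of the 65% survival in Section 11. It comes from the 1-to-7-day registry patients and serves only as a round figure. The synopsis gives about 50% as a second value. The share d of eventual deaths and the share s of eventual survivors who leave before 72 hours are assumptions; the documents give neither. No device effect is built in.

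**Mortality among those kept** = p(1-d) / [p(1-d) + (1-p)(1-s)]

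| d | s | Calculation at p = 35% | Result | Shift (points) |
|---|---|---|---|---|
| 20% | 10% | 0.280/(0.280 + 0.585) | 32.4% | -2.6 |
| 10% | 20% | 0.315/(0.315 + 0.520) | 37.7% | +2.7 |
| 20% | 20% | 0.280/(0.280 + 0.520) | 35.0% | 0 |
| 40% | 0 | 0.210/(0.210 + 0.650) | 24.4% | -10.6 |
| 0 | 40% | 0.350/(0.350 + 0.390) | 47.3% | +12.3 |

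The sign depends only on whether d or s is larger. The first three rows are the more natural cases, because death and improvement are both listed exits. The last two are extremes. At p = 50% the first two rows give 0.40/0.85 = 47.1% and 0.45/0.85 = 52.9%.

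**Effect of matching on duration.** Suppose that control for total treatment duration selects the registry patients with a fraction f of the same exit shares. The shifts in the table are the case f = 0. With f = 0.5:
- First row: controls become 0.315/(0.315 + 0.6175) = 33.8%, and the spurious difference is 32.4 - 33.8 = -1.4 points.
- Second row: controls become 0.3325/(0.3325 + 0.585) = 36.2%, and the difference is 37.7 - 36.2 = +1.5 points.

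With f = 1 the difference is zero. The absolute rate in SCD patients stays shifted in every case.

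**Dialysis dependency among survivors.** Let q be the true proportion dependent. If 20% of recovered survivors leave early, the result is q/[q + 0.8(1-q)]. The 10-20% non-recovery in the synopsis becomes 12.2-23.8%. If 20% of dependent survivors leave instead, 0.8q/[0.8q + (1-q)] gives 8.2-16.7%. Earlier SCD data point to a lower q: all survivors were dialysis-independent at day 60 in ARF-002 (Section 2.4), and 0/16 were dependent in the SCD-003 calcium-range subgroup (Section 2.5.3). At an assumed q of 2%, the first formula gives 2.5%.

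**Counts** (assumed numbers of deaths).
- Of the 16 patients in Section 10: 6/16 = 37.5% becomes 4/14 = 28.6% after two early deaths, or 6/14 = 42.9% after two early-leaving survivors.
- Of the maximum of 30 in Section 5.1: 10/30 = 33.3% becomes 8/28 = 28.6% after two early deaths, but stays at 8/24 = 33.3% if four survivors also leave.

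**What 72 hours means.** Section 11 does not say whether the hours are elapsed or on the device. With the interruption in Section 7.1 read as 12 hours in each 24, 72 device-hours could take up to 6 x 24 = 144 hours. Read as 12 hours in total, it is 72 + 12 = 84 hours. The separate 24-hour ECMO allowance comes on top. The documents do not settle which reading applies.

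**The case against.** The strongest reply is that this is a pilot. Section 11 says it is neither designed to assess efficacy nor powered, the registry comparison is offered only for insight, and no success criterion depends on it. The exact 95% interval for 6/16 runs from 15.2% to 64.6%, far wider than the mixed-exit shifts. This stands as a limit on severity. It does not remove the problem: low power concerns precision, whereas the 72-hour rule changes which patients the estimate describes.

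A second reply is that control for total treatment duration holds the registry patients to a similar course. It may offset part of the selection, as the f = 0.5 case shows. But duration is itself post-baseline, no common 72-hour landmark is set, the absolute rates are not repaired, and matching on adverse events adds another post-treatment variable.

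Third, eligibility screens out some early deaths (inclusion 5, exclusions 13 and 14). That is right, and it makes the case of 40% of deaths leaving an upper end.

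Some stronger readings are tempting and not supported:
- A reader might infer that the rule favours the device. Early recoveries are dropped as well as early deaths, so the sign is open.
- A reader might infer that early stoppers vanish from the safety data. Adverse events are recorded from enrollment (Section 9.7.2) and assessed for causality in all enrolled patients (Section 9.5). Since the rule is introduced partly on safety grounds and the final outcome analysis is not defined, its reach into the safety analysis is unclear, not established.
- A reader might infer that any device clotting excludes a patient. Section 7.1 and Appendix E provide for changing the device; only a problem that ends SCD before 72 hours would do so.
- A reader might infer that no outcome has any other analysis set. Appendix D gives one for renal recovery.

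**Conclusion.** The point holds. As written, the final outcome analysis selects patients on a post-treatment condition tied to the outcome, and no matching condition is stated for the controls. Mortality, dialysis dependency and their comparison with ppCRRT are open to bias of unknown direction. Under the mixed-exit assumptions the shift in mortality is about 2.6 points either way at 35% true mortality with no offset in the controls. It is smaller in the comparison if duration matching works in part, zero if the exit shares are equal, and 10 to 12 points only in one-sided extremes. All exit shares are assumed, so these figures show sensitivity and do not predict a result. The text should be corrected before outcome data are analysed. The lack of a success criterion limits the severity, while the intended use in designing a pivotal trial keeps it relevant.

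**What to change.** Amend Section 11 as follows.

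1. Make every patient who starts SCD, whatever the duration, the main set for mortality and dialysis dependency, and state the same set for safety.
2. In that main comparison, match or adjust only on factors known at CRRT initiation. Remove total treatment duration and adverse events from the two lists.
3. Keep the at-least-72-hour analysis as a labelled sensitivity analysis. State whether the hours are elapsed or on the device. Compare with registry patients alive and still on CRRT at 72 hours if the registry's timing data allow it; the documents do not show how finely timing is recorded.
4. Report how many patients did not reach 72 hours, with the primary reason for stopping that Section 7.2 already requires.

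**Cost.** The change is an edit to the 72-hour sentence and the two factor lists. No new trial data are needed, because Sections 7.1 and 7.2 keep early stoppers in follow-up unless consent is withdrawn. The price is a lower mean SCD exposure in the main set and a little extra registry work. A small difference from the registry remains and should be stated: SCD may start up to 12 hours into CRRT (Section 6.4), so some trial patients have already survived those hours at entry.
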